## 9.6.3. Pregnancies

Pregnancy of a female subject or the female partner of a male subject occurring while the subject is on study drug or within 4 weeks after the subject's last dose of study drug are considered expedited reportable events. If the subject is on study drug the study drug is to be discontinued immediately and the subject is to be instructed to return any unused portion of the study drug to the Investigator. Within 24 hours of the investigator's knowledge, all pregnancies must be reported to Celgene Corporation World Wide Safety Surveillance (WWDSS) by phone and facsimile.

The Investigator will follow the pregnant female until completion of the pregnancy, and must notify Celgene Corporation Worldwide Drug Safety Surveillance (WWDSS) of the outcome as specified below. The Investigator will provide this information as a follow-up to the initial SAE.

Page 53 of 86 Confidential

If the outcome of the pregnancy meets the criteria for immediate classification as a SAE

(i.e., spontaneous abortion [any congenital anomaly detected in an aborted fetus is to be

documented], stillbirth, neonatal death, or congenital anomaly), the Investigator should

follow the procedures for reporting SAEs (i.e., report the event to Celgene Corporation

Worldwide Drug Safety Surveillance (WWDSS) by facsimile within 24 hours of the

Investigator's knowledge of the event).

Any suspected fetal exposure to lenalidomide must be reported to Celgene within 24

hours of being made aware of the event. The pregnant female should be referred to an

obstetrician/gynecologist experienced in reproductive toxicity for further evaluation and

counseling.

All neonatal deaths that occur within 30 days of birth should be reported, without

regard to causality, as SAEs. In addition, any infant death after 30 days that the

investigator suspect is related to the in utero exposure to the study drug should also be

reported.

In the case of a live "normal" birth, Celgene Corporation Worldwide Drug Safety

Surveillance (WWDSS) should be advised as soon as the information is available.

## 9.7. Investigator Reporting Responsibilities

The conduct of the study will comply with all FDA safety reporting requirements. Given that the FDA has granted an IND exemption for this study, an annual report is not required.

All adverse experience reports must include the patient number, age, sex, weight, severity of reaction (mild, moderate, severe), relationship to study drug (probably related, unknown relationship, definitely not related), date and time of administration of test medications and all concomitant medications, and medical treatment provided. The investigator is responsible for evaluating all adverse events to determine whether criteria for "serious" and as defined above are present. The investigator is responsible for reporting adverse events to Celgene as described below.

#### 9.7.1. Expedited reporting by investigator to Celgene

Serious adverse events (SAE) are defined above. The investigator should inform Celgene of any SAE within 24 hours of being aware of the event. This must be documented on Celgene SAE form, an acceptable institution SAE from or a FDA 3500 or MEDWATCH form. This form must be completed and supplied to Celgene within 24 hours of the investigator's knowledge of the event. The date of awareness should be noted on the report. The initial report must be as complete as possible, including details of the current illness and (serious) adverse event, and an assessment of the causal relationship between the event and the investigational product(s), if available. Information not available at the

Page 55 of 86 Confidential

time of the initial report (e.g., an end date for the adverse event or laboratory values received after the report) must be documented on a follow-up MEDWATCH. A final report to document resolution of the SAE is required. The Celgene protocol number (RV-MM-PI-0454) should be included on SAE reports to Celgene. A copy of the fax transmission confirmation of the SAE report to Celgene should be attached to the SAE and retained with the patient records.

Moffitt Cancer Center will only be responsible to report to Celgene those events that occur at Moffitt.

## 9.7.2. Report of Adverse Events to the Institutional Review Board

The principal Investigator is required to notify his/her Institutional Review Board (IRB) of a serious adverse event according to institutional policy.

## 9.7.3. Investigator Reporting to the FDA

Adverse drug reactions that are **Serious**, **Unlisted/unexpected**, **and at least possibly associated to the drug**, and that have not previously been reported in the Investigators brochure, or reference safety information document should be reported promptly to the Food and Drug Administration (FDA) in writing by each investigator/physician engaged

Page 56 of 86 Confidential

in clinical research. A clear description of the suspected reaction should be provided

along with an assessment as to whether the event is drug or disease related.

Adverse event updates/IND safety reports

Celgene for lenalidomide shall notify the Investigator via an IND Safety Report of the

following information:

• Any AE associated with the use of study drug in this study or in other studies that

is both serious and unexpected.

• Any finding from tests in laboratory animals that suggests a significant risk for

human subjects including reports of mutagenicity, teratogenicity, or

carcinogenicity.

The Investigator shall notify his/her IRB/EC promptly of these new serious and

unexpected AE(s) or significant risks to subjects.

The Investigator must keep copies of all AE information, including correspondence with

Celgene and the IRB/EC, on file (see Section 13.4 Study records requirements).

9.7.4. Efficacy assessments

9.7.4.1. Myeloma paraprotein

Serum and urine protein electrophoresis, quantitative immunoglobulins, serum and urine

immunofixation studies (see Section 2, Schedule of Study Assessments). Response will

be assessed using the Uniform response criteria set forth by the International myeloma

working group (IMWG) (See Appendix II). Response will be assessed at least every 3

months in the maintenance setting.

Version. 6 date 4/15/2016

Page 56 of 86 Confidential As of April 2016, given all patients are in maintenance, patients will be followed for follow up and survival. Response assessment is not mandated per the trial and per institutional standard of care and to occur at a minimum of every 3 months.

Page 57 of 86 Confidential

## 9.7.4.2. Bone marrow aspiration/ biopsy

At baseline, after 2 cycles of lenalidomide monotherapy, at the end of study, to confirm complete response, and as clinically indicated (see Section 2, Schedule of Study Assessments).

# 9.7.4.3. Skeletal survey

Radiographic assessment of the bones to be done at baseline, end of study, to confirm complete response, and as clinically indicated (see Section 2, Schedule of Study Assessments).

#### 9.7.5. Correlative and translational studies

All patients will be encouraged to participate in the correlative / translational studies outlined below. However, patients will have the option to decline such participation and still be eligible for inclusion in the study if they meet all other requirements and assessments. Correlatives / translational studies will involve additional bone marrow aspiration specimen (optimally up to 20 cc additional aspiration needed) and peripheral blood specimens. Bone marrow plasma cells from patients with multiple myeloma will be isolated with CD138 positive beads. RNA will be extracted and expression of tumor suppression genes will be assayed by real time reverse transcriptase polymerase chain reaction (RT-PCR) at baseline and after 2 cycles of mono-therapy with lenalidomide.

#### 9.7.5.1. Effects of Lenalidomide Monotherapy on Tumor Suppressor Genes

CD138 positive plasma cell will be isolated from the bone marrow aspirate of patients at diagnosis and after 2 cycles of lenalidomide using CD138 positive selection. RNA will be extracted. Quantitative PCR (Q-PCR) will be performed to

Page 58 of 86 Confidential

assay the expression of the following target genes: EGR1, EGR2, EGR3, p15, p21, p27 and SPARC. These studies will be performed by the Moffitt Core Lab under the direction of [name]. We estimate 15 paired samples will be obtained to compare the expression of the above mentioned genes pre and post 2 cycles of lenalidomide monotherapy.

## 9.7.5.2. Demonstration of Lenalidomide Induced Humoral Immune Response

Peripheral blood will be collected at the time of study start (C1D1), after 2 cycles of lenalidomide monthotherapy, at the time of addition of dexamethasone, and 2 cycles after the addition of dexamethasone. Serum will be used for the detection of lenalidomide induced humoral immune response using the serametrix assay. Samples will be stored at -20°C prior to assay in the lab of [name].

# 9.7.5.3. Effects of lenalidomide monotherapy and in combination with corticosteroids on T cells subsets

Peripheral blood collected at the time of study start (C1D1), after 2 cycles of lenalidomide monthotherapy, at the time of addition of dexamethasone, and 2 cycles after the addition of dexamethasone will be used for the determination of changes in T cell subsets with lenalidomide monotherapy and after the addition of dexamethasone. The determination of T cell subset will be performed by flow cytometry. Samples will be collected, processed (ficoll separation and slow freeze at -120°C) and stored under the care of [name]. A total of 5 green top tube per sample will be obtained.

Page 59 of 86 Confidential

9.7.5.4. Effects of single agent lenalidomide on global gene expression profile of malignant plasma cells.

RNA extracted from CD138 positive cells isolated from the bone marrow aspirate of patients with myeloma at baseline and after 2 cycles of lenalidomide monotherapy will be subjected to affymatrix array for global gene expression profiling and changes in gene expression before and after treatment will be correlated.

## 9.7.5.5. Significance of Notch signaling in myeloma

RNA will be isolated form CD138 positive cells and the expression of notch receptors, ligants and targets by Q-pCR will be compared among responder and non responders to lenalidomide. These experiments will be performed by [name].

9.7.5.6. Post Translational modification of protein drug targets in myeloma using mass spectrometry

Cell pellets of comprised of CD138 positive cells will be used for proteomic studies. Using quantitative mass spectrometry, protein expression and selected post-translational modifications will be monitored for apoptotic proteins, nuclear factor kappa B survival signaling, and existing drug targets. The impact of exposure to lenalidomide on the malignant cell proteome will thus be examined. These studies will be performed by [name].

## 9.7.5.7. Prioritization of samples for correlative/translational studies

Page 60 of 86 Confidential

Recognizing that not all patients will consent to the ancillary studies noted above and for some of the patients who do consent, the quantity of quality sample might not be sufficient for all experiments above, the following priority for sample usage for correlative studies is proposed (mainly applicable to bone marrow aspiration samples):

- 1- induction of tumor suppressor genes by lenalidomide
- 2- Post translational modification of protein drug targets in myeloma using mass spectrometry
- 3- Significance of Notch signaling in myeloma
- 4- Differential gene expression profile of malignant plasma cell treated in vivo with lenalidomide as monotherapy

## 10. Protocol Amendments/Deviations

#### 10.1. Protocol amendments

Any amendment to this protocol must be agreed to by the Principal Investigator and reviewed by Celgene. Amendments should only be submitted to IRB/EC after consideration of Celgene review. Written verification of IRB/EC approval will be obtained before any amendment is implemented.

## 10.2. Protocol deviations

When an emergency occurs that requires a deviation from the protocol for a subject, a deviation will be made only for that subject. The physician in attendance in such an emergency will, if circumstances and time permit, contact Principal Investigator ([name]

Page 61 of 86 Confidential

[name], MD) prior to the deviation immediately by telephone. If time does not allow for this, the Investigator will notify [name] of the deviation as soon as possible in writing and by phone.

Such contacts will be made as soon as possible to determine whether or not the subject (for whom the deviation from protocol was effected) is to continue in the study. The subject's medical records will completely describe the deviation from the protocol and state the reasons for such deviation and document the contact or attempted contact with [name]. In addition, the Investigator will notify the IRB/EC in writing of such deviation from protocol.

Non-emergency minor deviations from the protocol will be permitted only with prior agreement from the Principal Investigator.

# 11. Data Management

# 11.1. Study monitoring and auditing

## 11.2. Scientific Review Committee (SRC)

The Cancer Center maintains two full board Scientific Review Committees (SRC), meeting every other week (the first Wednesday and third Thursday of every month) as well as one Behavioral Ad-Hoc SRC.

Each SRC conducts a formal internal peer review of all clinical protocols and general scientific oversight of interventional clinical research. Protocols are reviewed for scientific merit, adequate study design, safety, availability of targeted study population, and feasibility of timely completion of all proposed research projects to be conducted by

Page 62 of 86 Confidential

its assigned programs at the Cancer Center. Each SRC is responsible for evaluating the risk/benefit assessment and corresponding data and safety monitoring plan as part of the scientific review and approval process. The SRC will refer any potential conflicts of interest identified in the proposed research to the Conflict Committee.

## 11.3. PI Responsibility

The PI of each study is ultimately responsible for every aspect of the design, conduct and actions of all members of the research team. This includes the final analysis of the protocol. The PI is responsible for ensuring that:

- All protocols include a DSMP and procedures for its implementation commensurate with the risk and complexity of the study. The DSMP must include a structured adverse event determination, monitoring and reporting system, including standardized forms and procedures for referring and/or treating subjects experiencing adverse events. The plan must include data and safety-monitoring procedures for subjects enrolled who may be receiving a part of their protocol-required treatment at community sites.
- In all cases, the PI of the study will have primary responsibility for ensuring that the protocol is conducted as approved by the SRC and IRB. The PI will ensure that the monitoring plan is followed, that all data required for oversight of monitoring are accurately reported to a DSMB and/or to the PMC and IRB as required, that all adverse events are reported according to protocol guidelines, and that any adverse actions reflecting patient safety concerns are appropriately reported.

Page 63 of 86 Confidential

# 11.4. The Protocol Monitoring Committee (PMC)

The PMC monitors its assigned ongoing research protocols for: adverse event reporting, data and safety monitoring, and internal audit findings. The PMC, upon review of any agenda item, may approve the study for continuation, require revisions, suspend or close a protocol.

Investigators of studies, which are designated to be reviewed by the PMC for data and safety monitoring, shall provide a statistical report of the study's progress and summary of adverse events and deviations based on the phase of the study and the associated risk of the study or more often if applicable. The external DSMB (if applicable) shall forward its report for high-risk studies designated for external review at least annually or more often if applicable.

## 11.5. Research Compliance Division (RCD)

RCD of the Corporate Compliance Office is the coordinating center for internal audits of clinical trials conducted at the Cancer Center. The audit procedure is a formal, comprehensive, source document review of all clinical trials. External audit reports that meet the criteria of the internal audit may be accepted in lieu of an internal audit.

The (RCD) shall provide a report to the PMC of internal audit findings for PMC action. A representative of the RCD will be present to discuss the audits with the PMC. For cause audits will be discussed during an executive session of the PMC. Only members (voting and ex-officio) may attend this session.

Page 64 of 86 Confidential

## 11.6. Investigator responsibilities

Investigator responsibilities are set out in the ICH guideline for Good Clinical Practice and in the US Code of Federal Regulations.

Investigators, or designee, must enter study data onto a data collection system. The Investigator will permit study-related audits by Celgene or its representatives, IRB/EC review, and regulatory inspection(s) (e.g., FDA, EMEA, and TPP), providing direct access to the facilities where the study took place, to source documents, to the data collection system, and to all other study documents.

The Investigator, or a designated member of the Investigator's staff, must be available at some time during audits to review data and resolve any queries and to allow direct access to the subject's records (e.g., medical records, office charts, hospital charts, and study related charts) for source data verification. The data collection must be completed prior to any visits and be made available to the Celgene representatives so that the accuracy and completeness may be checked.

This study may be subject to an independent audit at the investigational site, which will be conducted by Celgene's Quality Assurance personnel or designee. Full consultation with appropriate personnel will be made prior to and during such an audit. The Investigator must be available during the audit.

If the Investigator is contacted by any regulatory authority regarding an audit for this study or any other study, the Investigator is to contact Celgene immediately.

## 12. Bio-statistical Consideration

This is a phase 2 trial evaluating a lenalidomide based response adapted strategy in older adults with newly diagnosed multiple myeloma. Descriptive statistics will be Version. 6 date 4/15/2016

Page 65 of 86 Confidential

used to summarize patients' demographic and clinical characteristics collected at each visit. Mean, standard deviation and range will be calculated for continuous variables, and frequency and percentage will be generated for categorical variables. The distribution (frequency and percentage) of patients treated with single agent lenalidomide, lenalidomide + prednisone, and lenalidomide+low dose dexamethasone will be presented.

## 12.1. Sample size:

The primary endpoint is 12-month PFS for the overall response adaptive approach. Based on the E4A03 and SWOG 2032 studies, the 12-month PFS is approximately 70% for patients treated with lenalidomide low dose dexamethasone. The sample size determination is primarily based on the consideration of providing an estimate of the 12-month PFS with reasonable precision. We estimate the 12-month PFS in the response adapted approach is 85%. With a sample size of 60 evaluable patients (30 from Moffitt and 30 from sites in South Korea), its 95% confidence interval is 73.4-92.9%.

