## STUDY ENDPOINTS

#### **Primary:**

1- The 12-month progression free survival (PFS) of older adults with mildly symptomatic multiple myeloma treated on this response adapted approach (i.e. time from lenalidomide start to failure of lenalidomide and low dose dexamethasone)

Page 6 of 86 Confidential

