In addition, this study will evaluate the role of an alternative corticosteroid in combination with lenalidomide. Prednisone is known to be a better tolerated corticosteroid than dexamethasone without a compromise in the efficacy. This was seen in a recent report of a clinical trial by the national cancer institute of Canada study comparing melphalan prednisone to melphalan dexamethasone (grade 3 and 4 infections; 9 versus 15%, p=0.03)[18]. In addition, the intergroupe francais du myelome (IFM) had noted similar finding in older adults with newly diagnosed myeloma randomized to melphalan prednisone or dexamethasone based induction[19]. Both trials did not note a superiority of dexamethasone based induction to the prednisone based induction.

Page 26 of 86 Confidential

The primary endpoint of this study will be the progression free survival of patients treated with this response adapted approach. This is defined as the time from enrollment to failure of lenalidomide and low dose dexamethasone. Outcomes of this cohort of patients treated with this response adapted approach would be compared to patients treated with lenalidomide and low dose dexamethasone. If this response adapted approach results in similar or improved outcomes compared to therapy with lenalidomide and low dose dexamethasone, this approach would be favored since it likely result in less toxicity by using an overall lower dosage of corticosteroid.

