#### **12.2.** Efficacy evaluation

#### 12.2.1 Primary efficacy analysis

Progression free survival (PFS) is defined as the time from start of lenalidomide monotherapy to the first occurrence of disease progression or death on study from any cause, whichever occurs earlier. All treated patients will be included in efficacy endpoint analysis. Those patients who are treated on this trial but have not had a relevant event at the time of last follow-up will be included in the analyses of these endpoints as censored observations.

Page 66 of 86 Confidential

The primary endpoint is the point estimate of the 12-month PFS rate for the overall response adaptive approach. Number and percentage of patients who survived greater or equal to 365 days without disease progression will be summarized. The 95% confidence interval will be calculated using the exact binominal method. The PFS curves will be estimated by the Kaplan-Meier method. Median and its 95% confidence intervals will be estimated.

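### The 70% benchmark is PFS on lenalidomide–dexamethasone alone, but the stated primary event is failure of the strategy's last regimen, so the two figures do not count the same event

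*Combined protocol and SAP*

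**What the plan says.** Three places give the primary event as failure of the last regimen. The synopsis defines it as "time from lenalidomide start to failure of lenalidomide and low dose dexamethasone". Section 5 does the same. Section 6.2 uses the same event but starts the clock at enrolment. The study design in the synopsis fits this: a patient who progresses before receiving dexamethasone may have it added and remain on study, and only progression on Ld takes the patient off.

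Section 12.1 gives the reference figure: "Based on the E4A03 and SWOG 2032 studies, the 12-month PFS is approximately 70% for patients treated with lenalidomide low dose dexamethasone". Next to it stands the planning value of 85% for the strategy, with a 95% interval of 73.4–92.9% for 60 evaluable patients. On the purpose of the sample size it says: "The sample size determination is primarily based on the consideration of providing an estimate of the 12-month PFS with reasonable precision".

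Section 6.2 says the cohort will be compared with patients treated with Ld and states the consequence: if the strategy "results in similar or improved outcomes compared to therapy with lenalidomide and low dose dexamethasone, this approach would be favored".

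Section 12.2.1 departs from the other three places. It defines PFS as time from lenalidomide start to the earlier of first progression and death.

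**The concern.** For a patient who starts on Ld, PFS in its usual sense ends at the first progression or at death. Under the definition in the synopsis, Section 5 and Section 6.2, progression on single-agent lenalidomide or on lenalidomide–prednisone does not end the strategy's clock. The clock runs on through Ld, which is the comparator itself. A total over two or three regimens is then set beside the duration of one. Identical patients and complete data would not remove that difference.

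At stake is the inference in Section 6.2. A strategy whose every step controls disease for less time than first-line Ld could be read as similar or improved, and be favoured on that ground.

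**Working it through.** **The plan's own figure.** 85% of 60 is 51 patients. The exact (Clopper–Pearson) two-sided 95% interval for 51/60 is 73.4–92.9%, which matches Section 12.1 and the method in Section 12.2.1 ("The 95% confidence interval will be calculated using the exact binominal method"). The interval arithmetic is correct.

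**Inputs.** From Section 12.1: 70% for Ld and 85% for the strategy. The documents give no PFS for Ld after progression on lenalidomide in newly diagnosed patients, so every other input below is an assumption, shown as a range.

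**Model (illustrative).** T1 is the time from lenalidomide start to first progression. T2 is the time from Ld start to Ld failure. Both are exponential and independent, Ld starts at first progression, and nobody dies before Ld. Let p1 and p2 be the 12-month PFS on the first regimen and on Ld given afterwards, with λ = −ln(p) per year. The strategy's 12-month value is

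P(T1 + T2 > 12 months) = (λ1·p2 − λ2·p1)/(λ1 − λ2), or p(1 + λ) when p1 = p2 = p.

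**Cases at or above 70%:**
- 50/50: 0.5 × (1 + 0.693) = 0.847, essentially the planned 85%.
- 10/70: (2.303 × 0.7 − 0.357 × 0.1)/(2.303 − 0.357) = 1.576/1.946 = 0.810.
- 33.4/33.4: 0.334 × (1 + 1.097) = 0.700.

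**Cases below 70%, with Ld weaker after lenalidomide failure:**
- 10/50: (2.303 × 0.5 − 0.693 × 0.1)/(2.303 − 0.693) = 1.082/1.609 = 0.672.
- 30/30: 0.3 × (1 + 1.204) = 0.661.
- 10/30: (2.303 × 0.3 − 1.204 × 0.1)/(2.303 − 1.204) = 0.570/1.099 = 0.519.

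**How far the result depends on Ld after failure.** Since T1 cannot be negative, T1 + T2 is at least T2. If Ld after progression kept its 70%, and no first event were a death, the strategy could not fall below 70% however poor the first regimen. In that case 85% is reached with only about 23% of patients free of first progression at 12 months. If Ld after failure is 50%, first-regimen values of 20% to 70% give 73% to 91%. If it is 30%, they give 60% to 87%.

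**Effect of deaths before Ld.** Let a share d of first events be deaths. The value becomes p1 + (1 − d)(S − p1), where S is the value without deaths. For p1 = 30%, Ld at 70% (S = 0.868) and d = 30%: 0.30 + 0.70 × 0.568 = 0.698, just under 70%.

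**Under Section 12.2.1.** If the event is first progression or death, T2 drops out and the strategy's figure counts the same event as ordinary PFS. The mismatch disappears.

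**The case against.** The strongest reply is that Section 12.2.1, which would produce the reported number, already counts first progression or death. That stands to this extent: under that text there is no mismatch. But three other places, including the endpoint section, say otherwise. PFS on single-agent lenalidomide is listed as a separate secondary endpoint, and Section 12.2.5 times duration of response to progression on lenalidomide and dexamethasone. Both sit more easily with the last-regimen reading. Settling the conflict in favour of Ld failure while keeping the 70% would make the mismatch permanent.

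Second, time until Ld is exhausted is a coherent question when the aim is to spare corticosteroid, and for patients who start on Ld that time also ends at Ld failure. This stands as a reason to keep the endpoint. It does not make a similar percentage evidence of similar disease control, because patients on the strategy may already have progressed once or twice.

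Third, a reader might infer that the strategy must reach 70% by construction. The documents do not support that. Ld after failure keeps lenalidomide in patients who have just progressed on it. The only related figure is in Section 4.2.2: 10 of 30 non-responders responded when dexamethasone was added, in relapsed disease and at high dose. The study design also says only that patients who progress are eligible for dexamethasone, not that all start it at once.

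Fourth, a reader might infer that the sample size or a hypothesis test is compromised. Neither is. The primary objective is estimation, the sample size rests on precision, and no null value, error rate or test against 70% is stated.

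Finally, Section 12.1 does not define PFS in the benchmark studies. That it ends at first progression or death is the usual meaning, and is assumed here.

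**Conclusion.** The concern holds in a limited form. Under the definition in the synopsis, Section 5 and Section 6.2, the 85% and the 70% do not count the same event, and the inference in Section 6.2 cannot be drawn from setting them side by side. In the illustration the strategy's figure runs from 52% to 85% for the six pairs worked above. The 50/50 pair, worse than 70% at both steps, reaches the planned 85%, while three pairs fall below 70%. The size and even the presence of an advantage depend on how well Ld works after lenalidomide failure, which the documents do not quantify. The result rests on independent exponential times, Ld started at first progression, and PFS in its usual sense for the benchmark. The flaw lies in the comparison and what is concluded from it. The 60 patients and the 73.4–92.9% interval stand.

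**What to change.** In Sections 6.2, 12.1 and 12.2.1, with the synopsis and Section 5 brought into line:
- State which event the primary endpoint and the 85% refer to.
- Use time from lenalidomide start to first progression or death, as Section 12.2.1 already defines it, for any comparison with the 70% figure.
- Report time to failure of Ld, with its confidence interval, as a descriptive endpoint of the strategy.
- Do not draw the Section 6.2 inference from time to failure of Ld unless a benchmark counted the same way is supplied, that is, from start of treatment to failure of a later regimen.

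The cost is wording in the protocol and the report, and reporting two estimates instead of one from data already collected. Enrolment does not change. The downside is that the figure set against 70% will be less favourable to the strategy.
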